## INVESTIGATOR STUDY PLAN - REQUIRED

### 1. TITLE

*Assessing Visual Perception in High Anxiety Follow Up*

### 2. EXTERNAL IRB REVIEW HISTORY\*

*This submission represents the follow up portion of a study that was conducted at the University of Pittsburgh from 2019-2023. This study was approved by the University of Pittsburgh IRB in 2018. The study ID for that approval is STUDY19010289. The contact info for The University of Pittsburgh IRB is [contact]*

### 3. PRIOR APPROVALS:

*The broader study that includes this protocol was approved following scientific committee review at the University of Pittsburgh in 2018.*

#### ***Conflict of Interest (COI):***

*No one involved in this research has any actual or potential COI.*

#### ***Clinical Engineering Department:***

*N/A*

#### ***Biohazardous Agents:***

*N/A*

#### ***Radiation:***

*N/A*

#### ***Students as Subjects:***

*N/A*

#### ***Research Informatics Core:***

*N/A*

#### ***UMCCTS Protocol Review Committee (PRC)***

*N/A*

### 4. OBJECTIVES\*

*The purpose of this study is to characterize visual system function in individuals with high trait anxiety. The fMRI portion of this study has already been conducted elsewhere. The follow up portion of the study is designed to determine if fMRI data can be used to predict future quality of life and anxiety symptoms that will be assessed at follow up. We hypothesize that visual cortex functional coupling will explain more variance in quality of life and anxiety severity at six months post-scan than prefrontal-amygdala functional coupling.*

*A subset of individuals with high trait anxiety will also complete an emotional faces task (MicroExpressions Training Task, or METT) as well as a 12-month follow up visit. This is an exploratory aim of the study to determine feasibility of the METT. We also hypothesize that individuals who complete the METT will show more improvement in anxiety symptoms at 12-months post-scan than those who do not.*

*Previously, participants in this study consented to an assessment visit, an fMRI visit, and a six month follow up data collection conducted remotely. In this initial consent form, it was mentioned that a subset of qualifying participants would be asked to complete the METT and a 12-month post-scan survey. The Pitt IRB asked us to consent these people via a separate consent form when they completed their six-month follow-up data collection.*

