## INVESTIGATOR STUDY PLAN - REQUIRED

*The present IRB would thus cover participants who have completed the consent process at Pitt, as well as a subset of participants who have been consented up through their six-month follow-up data collection, who will need to be additionally consented for their 12-month data collection and the METT. Because the METT is randomly assigned to either 6-months or 12-months post scan, these participants will have to be consented at 6-months, as some of them will be asked to complete the METT at that time.*

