### 10. STUDY ENDPOINTS\*

[figure not shown]
The primary outcome measures will be 1) anxiety symptom severity, 2) self-reported quality of life (QLESQ form), 3) completion rate of the METT (feasibility)

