## INVESTIGATOR STUDY PLAN - REQUIRED

### 11. PROCEDURES INVOLVED\*

To assess the relative contributions of fMRI data to anxiety severity and QoL longitudinally, participants will repeat QoL and anxiety measures via online forms approximately six months post-scan visit. These self-report forms assess various facets of anxiety symptoms and quality of life. These measures include the Depression, Anxiety and Stress Scale (DASS), Mood Anxiety Symptoms Questionnaire (MASQ), Perceived Stress Scale (PSS), Sensory Over Responder Scale (SOR), Somatic Symptoms Scale (SSS), Spielberger State Trait Anxiety Inventory, STAI, Quality of Life Enjoyment and Satisfaction Questionnaire- Short Form (QLESQ), Profile of Mood State Questionnaire (POMS), and an update to their medication form in case there have been any changes to their medication usage.

As an Exploratory Aim designed to test the hypothesized mechanism for altered visual processing in HTA and its relation to future clinical and functional measures, individuals with HTA will be randomly assigned to complete a visual discrimination behavioral manipulation at either 6 months post scan or 12 months post scan. The behavioral manipulation is the Micro Expressions Training Tool (METT), a visual discrimination task that will be used to determine if the visual system is a tractable target for intervention. The METT presents images of micro expressions; participants receive real-time feedback following forced choice emotional identification. The METT includes a brief pre-test, training, and then a post-test. It takes approximately 75 minutes to complete. We will collect performance data, to include accuracy and rate of training. Emotional micro expressions are subtle, involuntary expressions that communicate emotion. Facial micro expression identification is trainable and associated with social behavior and psychological well-being. We will repeat collections of self-report data in the HTA participants approximately 12 months from the initial fMRI visit via online survey. This will allow us to assess possible intervention effects on anxiety symptom severity and QoL 12 months later.

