### 27. PROVISIONS TO PROTECT THE PRIVACY INTERESTS OF SUBJECTS

*Data collection will occur via secure online form. The link to this form will be emailed to participants. Participants can complete this online form at their discretion. All participant reminders and scheduling phone calls will occur in a private office setting at the Medical School Building. The medication form is not a part of the secure online form, and therefore data from that form will be collected over the phone, again, in a private office setting at the Medical School Building. Participants who are eligible for the METT will be scheduled for a Zoom call that will be conducted over the secure UMass network. This call will also be conducted in a private office setting. Participants will be reminded that they can skip any survey questions they do not wish to answer. Only information necessary for conducting the research will be collected. Because this is a follow up data collection, participants will have previously completed survey measures at their initial visit when they were enrolled in the study.*

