### **30. CONSENT PROCESS**

*All study staff will be trained in the informed consent process by the PI. This research constitutes the follow up portion of an existing study that was conducted at the University of Pittsburgh. For this study, all participants completed a baseline visit, an fMRI scan visit, and a 6 month survey. These three portions of the study were therefore included in a single consent form that was administered prior to any research procedures. However, a subset of participants (those with high trait anxiety) are asked to complete two additional procedures: a 12 month follow up survey, and the METT, which is administered with either the six month or the 12 month surveys. Of the participants with remaining follow up data collection, a small number of individuals with high trait anxiety still need to be consented for these procedures. All participants without high trait anxiety have already been consented for follow up, at the time of their enrollment.*

*We will consent the remaining high trait anxiety individuals for the follow up data collection remotely. It is not feasible to consent them in-person, given that they were recruited in Pittsburgh, PA. Therefore, the consent process will take place prior to follow-up data collection and will be conducted remotely, either over the phone or over Zoom. Participants will be given the opportunity to ask questions and to consider whether to continue their participation in the study.*

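### The METT hypothesis compares completers with non-completers, but only METT timing is randomised; the early-versus-deferred contrast is not stated and the survey order it needs is not fixed

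*Protocol*

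**What the plan says.** - **Hypothesis.** Protocol section 4 (Objectives) expects that "individuals who complete the METT will show more improvement in anxiety symptoms at 12-months post-scan than those who do not".
- **Randomisation.** The same section explains the consent timing with "Because the METT is randomly assigned to either 6-months or 12-months post scan". Section 11 (Procedures Involved) says HTA participants will be "randomly assigned to complete a visual discrimination behavioral manipulation at either 6 months post scan or 12 months post scan". Both arms are assigned the METT; only its date differs.
- **Who has 12-month data.** Section 11: "We will repeat collections of self-report data in the HTA participants approximately 12 months from the initial fMRI visit via online survey". Section 24 also limits the 12-month collection to participants with high trait anxiety.
- **METT and survey.** Section 30 (Consent Process) describes "the METT, which is administered with either the six month or the 12 month surveys". Section 27 says of the emailed survey, "Participants can complete this online form at their discretion", and separately, "Participants who are eligible for the METT will be scheduled for a Zoom call".
- **Endpoints and analysis.** Section 10 lists "completion rate of the METT (feasibility") among the primary outcome measures. Section 13 says the exploratory aim is not designed for significance testing, will focus on effect sizes and is to provide pilot data for grant submissions. Neither section 11 nor section 13 names the groups to be compared.

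**The concern.** The stated hypothesis and the stated randomisation do not match. A person outside the completer group is either someone who was assigned the METT and did not do it, or someone in the 12-month arm who has not yet done it when surveyed.

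On the first meaning the comparison is not randomised. People select themselves into it after assignment, and completion is itself the feasibility endpoint, so the better feasibility turns out, the smaller the comparison group becomes. Late-arm completers would also sit in the treated group although they have no follow-up after the METT.

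The second meaning gives a proper randomised contrast, early versus deferred METT. The protocol does not state it, and it works only if the late arm answers its 12-month survey before its METT.

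At stake is the effect size that this aim exists to supply. Leaving out a significance test does not protect an effect size from self-selection or dilution. The same unfixed order also arises at six months, where the survey supplies the outcome for the main fMRI-prediction hypothesis.

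**Working it through.** **1. The plan's own figure.** None is given for the METT contrast. The 91% power in section 13 belongs to the main regression. It reproduces (noncentrality 0.15 × 75 = 11.25, one tested term, 8 predictors, 66 residual df, power 0.911, with two-sided alpha 0.05 assumed) and does not bear on this point.

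**2. Who could form the comparison group.**
- Participants without HTA: no, they have no 12-month survey.
- HTA participants who decline the additional consent: no, that consent covers both the METT and the 12-month survey (sections 4 and 30), so they have neither.
- HTA participants who consent but do not do the METT: yes, but self-selected.
- Late-arm participants surveyed before their METT: yes, and randomised, but only if that order holds.

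**3. Is the order fixed?** Section 30 says only that the METT goes with the surveys. Section 27 leaves the survey to the participant and puts the METT on a separate call. Nothing says which comes first. At six months, section 4 suggests that at Pittsburgh the extra consent came when the six-month collection was completed, which points to survey first. Section 30, however, places the remaining consents before follow-up data collection, so for those participants consent timing no longer implies an order.

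**4. Precision (illustration).** Input from section 13: 30 planned HTA participants. Assumed: all 30 enter, split 15 v 15, all give 12-month data, no covariate adjustment. Half-width in SD = t(0.975, 28 df) × √(1/n₁ + 1/n₂), with t = 2.048.

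| Contrast | n₁ v n₂ | Half-width (SD) |
|---|---|---|
| As randomised | 15 v 15 | 2.048 × 0.365 = 0.75 |
| Completers v not, 10% non-completion | 27 v 3 | 2.048 × 0.609 = 1.25 |
| 20% | 24 v 6 | 2.048 × 0.456 = 0.93 |
| 30% | 21 v 9 | 2.048 × 0.398 = 0.82 |
| 0% | 30 v 0 | undefined |

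The loss is large only when non-completion is low.

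**5. Dilution (illustration, assuming no selection).** Let d be the METT effect at 12 months in someone who did it at 6 months.
- *Literal contrast.* If late-arm completers show no effect yet, the contrast equals f × d, where f is the early-arm share of completers: 0.5d when the arms complete equally, 0.4d to 0.6d for f from 0.4 to 0.6.
- *As-randomised contrast.* With non-completion p, share q of late-arm completers surveyed after the METT, and immediate effect r × d, it equals (1 − p)(1 − q·r)d. At p = 0.2 this is 0.80d for q = 0; 0.8 × 0.75 = 0.60d for q = r = 0.5; 0.8 × 0.5 = 0.40d for q = 0.5, r = 1; and 0 for q = r = 1.

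The protocol gives no basis for p, q or r, so these are ranges. The last case is extreme: it needs every late-arm survey to follow the METT and a full effect straight after one session of about 75 minutes.

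**The case against.** The strongest reply is that random assignment to 6 or 12 months followed by a 12-month survey is an ordinary deferred-treatment design, and that the hypothesis simply means those who have not done the METT by then. That is probably the intent. It answers the charge of self-selection if the analysis follows it, but no section says so, and it leaves the survey order open.

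A second reply is that analysis as randomised, baseline adjustment and intervals belong in a statistical analysis plan, and the order in an operations manual. This is partly right: those details alone would be no finding. What remains is a protocol hypothesis that names a different contrast from the one randomised.

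A third reply is that the illustration is weak. It assumes arm sizes and completion and models no selection, and 30 may be an upper limit, since section 4 speaks of a subset of HTA participants while section 30 takes the subset to be all of them. That stands. The figures show precision and dilution, not the size of any selection bias.

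A reader might also infer that the main fMRI-prediction outcome is contaminated by the METT. The documents do not support that: they leave the six-month order open, and section 4 suggests survey first at Pittsburgh. Nor do they support declaring that aim unaffected.

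**Conclusion.** The point holds as a mismatch between hypothesis and design plus an unfixed measurement order. Taken literally, the hypothesis gives up the randomisation, counts late-arm completers as treated and has no comparison group if everyone completes. The likely intended contrast is sound but unstated, and the stated procedures do not secure it.

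A reader might go further and conclude that the aim has no valid control, or that its estimate will be biased by a known amount. Neither follows: the early-versus-deferred comparison is available from the randomisation, and the documents give no data on completion, order or selection.

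Severity is low to moderate. The aim is exploratory pilot work without significance testing, and even the randomised contrast would carry an interval of about ±0.75 SD under the 15 v 15 assumption. The six-month order deserves the same attention because that survey feeds the main hypothesis.

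**What to change.** 1. Restate the section 4 hypothesis and the section 13 effect-size comparison as HTA participants randomised to METT at 6 months versus at 12 months, analysed as randomised regardless of completion, on 12-month anxiety adjusted for the initial-visit score (section 27 confirms that survey measures were taken then). Report the effect size with its 95% CI.
2. Keep completer comparisons descriptive, beside the section 10 completion rate.
3. State that the survey at each time point is submitted before that time point's METT call.
4. For participants already followed up, check the order where dates were recorded, and report how many surveys followed the METT or have unknown order. Section 26 lists only accuracy and completeness among METT data, so dates may be lacking, and a date alone cannot settle same-day order.

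**Cost.** Some wording, one stated order and a date check; no new participants or measures. Only 16 participants have follow-up outstanding and only some are HTA, so the order can still be set for few. The downside is that the as-randomised estimate may be somewhat smaller than one comparing early-arm completers with people not yet treated: 0.9d, 0.8d and 0.7d against d at 10, 20 and 30% non-completion, with the order held and no selection.

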## INVESTIGATOR STUDY PLAN - REQUIRED

*The present IRB would thus cover participants who have completed the consent process at Pitt, as well as a subset of participants who have been consented up through their six-month follow-up data collection, who will need to be additionally consented for their 12-month data collection and the METT. Because the METT is randomly assigned to either 6-months or 12-months post scan, these participants will have to be consented at 6-months, as some of them will be asked to complete the METT at that time.*

### 5. BACKGROUND\*

*Individuals with high trait anxiety (HTA) have elevated fear responses to threatening situations and are more likely to react with nervousness or apprehension to a broad range of situations that may not be threatening. HTA is a stable individually differing feature and trans-diagnostic risk factor for the development of a range of chronic illnesses and conditions, most prominently mood and anxiety disorders. HTA is also associated with poor functional outcomes in psychiatric disorders, such as reduced quality of life (QoL). However, the neurobiological underpinnings of HTA remain unclear. Identification of modifiable mechanisms that underlie HTA is critical given that HTA is a behavioral marker that often precedes the onset of psychiatric disorders and is associated with significant illness burden and suffering.*

*HTA is characterized by heightened sensitivity to threat or potential threat. Because of the primacy of social visual information for humans, the anxiety literature emphasizes social stimuli such as novel faces (potential threat) and emotional faces. Individuals with anxiety disorders misattribute threat to neutral stimuli, overestimate threat, and identify faces as threatening at lower emotional expression intensities relative to individuals without HTA.*

*In the traditional, top-down anxiety model, this bias is believed to be due to incorrect stimulus contextualization, mediated by prefrontal cortex (PFC) projections to the amygdala. However, the role of both bottom-up and top-down processes in visual perception has long been recognized. Taken together, there is ample evidence for a reduced perceptual threshold in HTA that cannot be explained by the received top-down model. Rather, such findings suggest that misattribution of threat or “diminished threat selectivity” in HTA includes a bottom-up sensory mechanism.*

*Enhanced visual cortex activation in response to novel or emotional stimuli is not solely dependent on top-down processes. Enhanced amplitude of the earliest visual waveform components in response to novel or emotional stimuli is well-established. The dual processing model posits that both bottom-up, implicit visual perception, and top-down, effortful attention, contribute to stimulus perception. In top-down processing, stimuli are attended because of effortful control that is often goal-directed. This process is facilitated by PFC projections to the amygdala and parietal cortex. In contrast, bottom-up implicit perceptual processes, facilitated by sensory cortices and the amygdala, are preattentive.*

*Perceptual alterations in HTA occur in a variety of contexts, indicating a generalized early processing mechanism. Although the literature has focused almost exclusively on fearful and angry face perception, perceptual processing of positive stimuli is also heightened in HTA and correlates with visual cortex function. The neural correlates of viewing more subtle emotional expressions in HTA, however, have not been investigated. Social interactions in the real world require interpretation of subtle emotional cues. Studies of subtle expressions created via emotional expression morphs are more naturalistic and would probe for a neural mechanism for reduced threat attribution threshold in HTA. By assessing visual cortex response to social and nonsocial stimuli that vary in their novelty or emotional intensity, we will test our hypothesis that HTA is characterized by enhanced visual cortex activity and bottom-up functional coupling to the amygdala, and that this functional alteration persists in a variety of contexts. If individuals with HTA show enhanced responsiveness to nonsocial stimuli, this would indicate generalized alterations in visual processes. Implicit, preattentive visual processing is designed to detect potential threats or rewards and occurs at an earlier latency than top-down processing, which provides context for*

## INVESTIGATOR STUDY PLAN - REQUIRED

stimuli. Thus, alterations in bottom-up processing would likely occur in response to a broad range of stimulus types. Observation of a generally elevated response would support the hypothesis that heightened reactivity in HTA is preattentive, implicit, and facilitated by an early bottom-up mechanism. Because the extant fMRI literature has focused nearly exclusively on threatening social stimuli, we are currently limited in our ability to answer questions about the function of the visual system in HTA and its relationship to processing in general as opposed to threat processing specifically.

### 6. INCLUSION AND EXCLUSION CRITERIA\*

This portion of the study will be conducted on participants who have already been recruited, screened, and enrolled in the study at another site. The exclusion criteria for recruitment were:

1) estimated IQ<70, 2) contraindication to MRI (including metal implants or devices in the body, pregnancy, claustrophobia), 3) history of head trauma or loss of consciousness, 4) major medical or neurological illness 5) current psychiatric medication usage or use in the last three months, 6) alcohol/substance abuse or dependence and/or illicit substance use (excepting cannabis) in the last three months, determined by Structured Clinical Interview for DSM-IV (SCID), 7) history of mania or psychosis

This study does not include individuals who are not yet adults, as it was designed to assess visual system function in adults. Pregnancy was an exclusion criteria at the time of study enrollment because of MRI contraindications. No prisoners or adults lack capacity to consent are included in this study. No one who is a non-English speaker will be included, as all study instruments and instructions are in English and have not necessarily been validated in other languages.

Because this is the follow up portion of this study, it is possible that some participants may have become pregnant in the intervening months since they completed their fMRI scan. Because this is a phone and teleconference based follow up study that involves answering self-report questionnaires, there are no risks specifically associated with pregnancy. We will not be collecting information related to pregnancy status for the remainder of the study. Similarly, it is possible that participants may have begun taking psychiatric medication in the intervening months since they were first enrolled in the study. This is not an exclusion criterion for the follow up portion of this study, as this study was designed to be a naturalistic study of high trait anxiety. Therefore, participants were not instructed to change their behavior regarding treatment/seeking treatment while enrolled in this study.

